5.6.3 Supportive Care for Trametinib

Rash is a frequent AE observed in subjects receiving trametinib (see the Investigator Brochures for more information). Recommendations for supportive care and guidelines for dose modifications for rash are based on experience with other MEK inhibitors[9] and EGFR inhibitors[10] and are provided in the table below and in the dose modification section for rash. Additional supportive care guidelines for trametinib and pembrolizumab are included in the dose modification guidelines in section 5.2.

Table 17. Guidelines for Supportive Care of Rash from Trametinib

Type of Care	Action				
	Avoid unnecessary exposure to sunlight				
Prevention /Prophylaxis ^a	• Apply broad-spectrum sunscreen (containing titanium dioxide or zinc oxide) with a skin protection factor (SPF) ≥15 at least twice daily.				
	Use thick, alcohol-free emollient cream (e.g., glycerine and cetomacrogol cream) on dry areas of the body at least twice daily.				
	Topical steroids and antibiotics should be applied at least twice daily starting on Day 1 of study treatment, to body areas such as face, chest, and upper back.				
	Use mild-strength topical steroid (hydrocortisone 1% cream) or topical antibiotic (e.g., clindamycin) or oral antibiotics (e.g., doxycycline 100 mg BID, minocycline 100 mg BID)				
	Pruritic lesions: cool compresses and oral antihistamine therapies				
Symptomatic	Fissuring lesions: Monsel's solution, silver nitrate, or zinc oxide cream				
Care ^b	Desquamation: thick emollients and mild soap				
	Paronychia: antiseptic bath, local potent corticosteroids in addition to oral antibiotics; if no improvement, consult dermatologist or surgeon				
	Infected lesions: appropriate bacterial/fungal culture-driven systemic or topical antibiotics				

Abbreviations: BID = twice daily; SPF = sun protection factor

5.7 Diet/Activity/Other Considerations

5.7.1 Diet

Subjects should maintain a normal diet unless modifications are required to manage an AE such as diarrhea, nausea or vomiting.

5.7.2 Contraception

Pembrolizumab may have adverse effects on a fetus in utero. Furthermore, it is not known if pembrolizumab has transient adverse effects on the composition of sperm.

a Rash prophylaxis is recommended for the first 6 weeks of study treatment

b Subjects who develop rash/skin toxicities should be seen by a qualified physician and should receive evaluation for symptomatic/supportive care management

For this trial, male subjects will be considered to be of non-reproductive potential if they have azoospermia (whether due to having had a vasectomy or due to an underlying medical condition).

Female subjects will be considered of non-reproductive potential if they are either:

(1) postmenopausal (defined as at least 12 months with no menses without an alternative medical cause; in women < 45 years of age a high follicle stimulating hormone (FSH) level in the postmenopausal range may be used to confirm a post-menopausal state in women not using hormonal contraception or hormonal replacement therapy. In the absence of 12 months of amenorrhea, a single FSH measurement is insufficient.);

OR

(2) have had a hysterectomy and/or bilateral oophorectomy, bilateral salpingectomy or bilateral tubal ligation/occlusion, at least 6 weeks prior to screening;

OR

(3) has a congenital or acquired condition that prevents childbearing.

Female and male subjects of reproductive potential must agree to avoid becoming pregnant or impregnating a partner, respectively, while receiving study drug and for 120 days after the last dose of study drug by complying with one of the following:

(1) practice abstinence[†] from heterosexual activity;

OR

(2) use (or have their partner use) acceptable contraception during heterosexual activity.

Acceptable methods of contraception are[‡]:

Single method (one of the following is acceptable):

- intrauterine device (IUD)
- vasectomy of a female subject's male partner
- contraceptive rod implanted into the skin

Combination method (requires use of two of the following):

- diaphragm with spermicide (cannot be used in conjunction with cervical cap/spermicide)
- cervical cap with spermicide (nulliparous women only)
- contraceptive sponge (nulliparous women only)
- male condom or female condom (cannot be used together)
- hormonal contraceptive: oral contraceptive pill (estrogen/progestin pill or progestin-only pill), contraceptive skin patch, vaginal contraceptive ring, or subcutaneous contraceptive injection

†Abstinence (relative to heterosexual activity) can be used as the sole method of contraception if it is consistently employed as the subject's preferred and usual lifestyle and if considered acceptable by local regulatory agencies and ERCs/IRBs. Periodic abstinence (e.g., calendar, ovulation, sympto-thermal, post-ovulation methods, etc.) and withdrawal are not acceptable methods of contraception.

‡If a contraceptive method listed above is restricted by local regulations/guidelines, then it does not qualify as an acceptable method of contraception for subjects participating at sites in this country/region.

Subjects should be informed that taking the study medication may involve unknown risks to the fetus (unborn baby) if pregnancy were to occur during the study. In order to participate in the study subjects of childbearing potential must adhere to the contraception requirement (described above) from the day of study medication initiation (or 14 days prior to the initiation of study medication for oral contraception) throughout the study period up to 120 days after the last dose of trial therapy. If there is any question that a subject of childbearing potential will not reliably comply with the requirements for contraception, that subject should not be entered into the study.

5.7.3 Use in Pregnancy

If a subject inadvertently becomes pregnant while on treatment with pembrolizumab and/or trametinib, the subject will immediately be removed from the study. The site will contact the subject at least monthly and document the subject's status until the pregnancy has been completed or terminated. The outcome of the pregnancy will be reported to the Sponsor Investigator and to Merck and to Novartis without delay and within 24 hours to the Sponsor Investigator and within 2 working days to Merck and Novartis if the outcome is a serious adverse experience (e.g., death, abortion, congenital anomaly, or other disabling or life-threatening complication to the mother or newborn).

The study investigator will make every effort to obtain permission to follow the outcome of the pregnancy and report the condition of the fetus or newborn to the Sponsor Investigator, Merck and Novartis. If a male subject impregnates his female partner the study personnel at the site must be informed immediately and the pregnancy reported to the Sponsor Investigator and to Merck and to Novartis and followed as described above and in Section 7.2.2.

5.7.4 Use in Nursing Women

It is unknown whether pembrolizumab is excreted in human milk. Since many drugs are excreted in human milk, and because of the potential for serious adverse reactions in the nursing infant, subjects who are breast-feeding are not eligible for enrollment.

5.8 Subject Withdrawal/Discontinuation Criteria

Subjects may withdraw consent at any time for any reason or be dropped from the trial at the discretion of the investigator should any untoward effect occur. In addition, a subject may be withdrawn by the investigator or the Sponsor Investigator if enrollment into the trial is inappropriate, the trial plan is violated, or for administrative and/or other safety reasons. Specific details regarding discontinuation or withdrawal are provided in Section 7.1.3 – Other Procedures.

A subject must be discontinued from the trial for any of the following reasons:

- The subject or legal representative (such as a parent or legal guardian) withdraws consent.
- Confirmed radiographic disease progression

Note: For unconfirmed radiographic disease progression, please see Section 5.2.2

Note: A subject may be granted an exception to continue on treatment with confirmed radiographic progression if clinically stable or clinically improved.

- Unacceptable adverse experiences as described in Section 5.2.1.2
- Intercurrent illness that prevents further administration of treatment
- Investigator's decision to withdraw the subject
- The subject has a confirmed positive serum pregnancy test
- Noncompliance with trial treatment or procedure requirements
- The subject is lost to follow-up
- Completed 24 months of uninterrupted treatment with pembrolizumab. Trametinib may be continued longer.

Note: 24 months of pembrolizumab is calculated from the date of first dose.

Administrative reasons

The End of Treatment and Follow-up visit procedures are listed in Section 6 (Study Calendar) and Section 7.1.4 (Visit Requirements). After the end of treatment, each subject will be followed for 30 days for adverse event monitoring (serious adverse events will be collected for 90 days after the end of treatment as described in Section 7.2.3.1). Subjects who discontinue for reasons other than progressive disease will have post-treatment follow-up for disease status until disease progression, initiating a non-study cancer treatment, withdrawing consent or becoming lost to follow-up. After documented disease progression each subject will be followed by telephone for overall survival until death, withdrawal of consent, or the end of the study, whichever occurs first.

5.8.1 Discontinuation of Study Therapy after CR

Discontinuation of treatment may be considered for subjects who have attained a confirmed CR that have been treated for at least 24 weeks with pembrolizumab and had at least two treatments with pembrolizumab beyond the date when the initial CR was declared.

5.9 Subject Replacement Strategy

N/A

5.10 Clinical Criteria for Early Trial Termination

Early trial termination will be the result of the criteria specified below:

- 1. Quality or quantity of data recording is inaccurate or incomplete
- 2. Poor adherence to protocol and regulatory requirements
- 3. Incidence or severity of adverse drug reaction in this or other studies indicates a potential health hazard to subjects
- 4. Plans to modify or discontinue the development of the study drug

In the event of Merck's or Novartis' decision to no longer supply study drugs, ample notification will be provided so that appropriate adjustments to subject treatment can be made.

6.0 STUDY CALENDAR

Time Period:	Screening Phase	e Treatment Cycle ¹		End of Treatment		Post-Treatment							
	Main Study Screening (Visit 1)	1	2	3	4	b		repea l 8 cy	eles	Discontinuation Visit	Safety Follow-up 30 days Post	Follow- up ¹⁵	Survival Follow-
Treatment Cycle/Title:	sereening (visit 1)					5	6	7	8	VISIT			
Scheduling Window (Days):	-28 to -1		± 3	± 3	± 3	± 3	± 3	± 3	± 3	At time of Discontinuation Discontinuation Discontinuation		1	up ¹⁶
Administrative Procedures													
Informed Consent	X												X
Inclusion/Exclusion Criteria	X												
Demographics and Medical History	X												
Prior and Concomitant Medication Review	X												
Trial Treatment Administration ⁸		X	X	X	X	X	X	X	X				
Survival Status		X				Ongo	ing			X	X	X	X
Clinical Procedures/Assessments ^{1,2}													
Review Adverse Events		X			(Ongoi	ng			X	X		
Full Physical Examination	X												
Directed Physical Examination		X^1	X	X	X	X	X	X	X	X	X		
Vital Signs, Weight and Height (height only at screening).	X	X^{l}	X	X	X	X	X	X	X	X	X		
ECOG Performance Status	X	X	X	X	X	X	X	X	X	X	X		
Ophthalmology Exam ¹¹	X					As cl	inical	ly ind	icated				
ECG ¹³	X	X	X	X					X				
ECHO/MUGA ¹²	X				X				X				
Laboratory Procedures/Assessments ^{5,6}	-10 to -1												
Pregnancy Test – Urine or Serum β-HCG ³	X												
PT/INR and aPTT ⁴	X												
CBC with Differential	X		X	X	X	X	X	X	X	X	X		
Comprehensive Serum Chemistry Panel	X		X	X	X	X	X	X	X	X	X		
Urinalysis	X												
T3, FT4 and TSH	X		X		X		X		X	X	X		
Efficacy Measurements													
Tumor Imaging ⁷	X		Every	9 we	eks w	vhile (on tre	atmen	ıt	X	X	X	
Tumor Biopsies/Archival Tissue Collection/Cor	relative Studies Blood												
Archival or Newly Obtained Tissue Collection ⁹	X	X								X			
Correlative Studies Blood Collection ¹⁰	X	X	X	X	X	X	X	X	X	X			

UCDCC#259 v.Original (05/09/2017)

- 1. In general, assessments/procedures are to be performed on Day 1 and prior to the first dose of trial treatment for each cycle unless otherwise specified. Treatment cycles are 3 weeks (21-days); however the pembrolizumab (MK-3475) treatment cycle interval may be increased due to toxicity according to the dose modification guidelines provided. If treatment cycles are increased all procedures except imaging will be completed according to the Cycle number and not weeks on treatment, imaging will be performed every 9 weeks (± 3 days) from the first dose of trial treatment regardless of any treatment delays. Weekly visits will also occur for the first cycle when starting trametinib (when trametinib is added (Cohort A C1D1, Cohort B C2D1). The first cycle where both drugs are given requires weekly clinic visits for review of adverse events, vital signs, ECOG performance status, directed physical exam and CBC and CMP.
- 2. In general, the window for each visit is ± 3 days unless otherwise specified.
- 3. For women of reproductive potential, a urine or serum pregnancy test will be performed within 72 hours prior to first dose of trial treatment. If urine pregnancy results cannot be confirmed as negative, a serum pregnancy test, performed by the local study site laboratory, will be required. Pregnancy tests (serum and/or urine tests) should be repeated if required by local guidelines.
- 4. Coagulation factors (PT/INR and aPTT) should be monitored closely throughout the trial for any subject receiving anticoagulant therapy.
- 5. Laboratory tests for screening are to be performed within 10 days prior to the first dose of trial treatment. See Table 19 for a list of specific laboratory procedures/assessments to be performed in this study.
- 6. After Cycle 1, lab samples can be collected up to 72 hours prior to the scheduled time point. Laboratory results must be known and acceptable prior to dosing.
- 7. The initial tumor imaging will be performed within 30 days prior to the first dose of trial treatment. Scans performed as part of routine clinical management are acceptable for use as the screening scan if they are of diagnostic quality and performed within 30 days prior to the first dose of trial treatment. On-study imaging will be performed every 9 weeks (63 ±7 days) after the first dose of trial treatment or more frequently if clinically indicated. The timing for imaging studies should follow calendar days and should not be adjusted for delays in cycle starts or extension of pembrolizumab /trametinib cycle frequencies. The same imaging technique should be used in a subject throughout the trial. CT including the chest, abdomen and pelvis or PET-CT is required for the baseline assessment. Patients who discontinue for reasons other than progression will be followed by imaging every 9 weeks.
- 8. Pembrolizumab (MK-3475) can be administered for up to 2 years. For the dose escalation and expansion Cohort (Arm) A (concurrent trametinib and pembrolizumab (MK-3475) both drugs will be administered as outlined in this protocol starting with cycle #1. For cohort B. trametinib will be initiated with cycle #1 and pembrolizumab (MK-3475) will commence in combination with trametinib starting with cycle #2, for Cohort C pembrolizumab (MK-3475) will be given for cycle 1 with concurrent trametinib added on C2D1.
- 9. Tumor biopsy for immune and molecular biomarker analysis will be performed prior to Cycle 1 of treatment either on archival tissue or fresh biopsy (within 6 months—no intervening treatment). Repeat biopsy will be performed on cycle 1 D11-13 or within 2 days after the last dose of trametinib for Arm A) and an optional end of study biopsy (within 28 days after progression).
- 10.Correlative blood draws for immune correlates will be performed prior to cycle 1 (- 3 days), prior to cycle 4 (-3 days), prior to cycle 7 (-3 days) and at discontinuation visit (± 5 days). Correlative blood draws for plasma DNA/RNA will be performed at baseline (cycle 1, day 1 prior to dosing or prior during screening), prior to each cycle of treatment (prior to concurrent administration of trametinib and pembrolizumab), and at progression (± 5 days).
- 11. Ophthalmology Exam: Indirect fundoscopic examination, visual acuity (corrected), visual field examination, tonometry, and direct fundoscopy within 6 weeks prior to registration.
- 12. ECHO/MUGA will be performed every 12-16 weeks unless clinically indicated. The same study should be used for follows that was done for the baseline exam.
- 13. EKG at baseline, C1D1, C2D1, C3D1. Then every 12-16 weeks unless clinically indicated.
- 14. Safety Follow-Up Visit should be conducted approximately 30 days after the last dose of trial treatment or before the initiation of a new anti-cancer treatment, whichever comes first.15. Subjects who discontinue trial treatment for a reason other than disease progression will move into the Follow-Up phase and should be assessed every 9 weeks (63 ±7 days) by radiologic imaging to monitor disease status.
- 16. Once a patient has progression, they will be followed every 12 weeks until death or withdraw from follow-up.

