5.2 Trial Treatments

The treatment to be used in this trial is outlined below in Table 2.

Table 2. Trial Treatments

Drug	Dose/Potency	Dose Frequency	Route of Administration	Regimen/Treatment Period	Use
Pembrolizumab (MK-3475)	200 mg	Q3W	IV infusion	Day 1 of each 3 week cycle	Experimental
Trametinib	x mg†	Daily†	PO	Daily starting D1	Experimental
† See dose escalation schema. RP2D for expansion cohorts.					

Dose Escalation Cohort (Arm A): Trametinib will be adminstered starting C1D1 and continued as per Table 3, until determination of the MTD. Pembrolizumab will be added to trametinib starting C2D1.

Dose Escalation Cohort (Arm B): Pembrolizumab will be administered starting C1D1 and trametinib will be added to pembrolizumab starting C2D1.

Expansion Cohort (Arm) A: Trametinib will be administered starting C1D1 and pembrolizumab will be added to trametinib starting C2D1 at the MTD of the combination as determined from the dose escalation portion of the study.

Expansion Cohort (Arm) B: Pembrolizumab will be administered starting C1D1 and trametinib will be added to pembrolizumab starting C2D1 at the MTD of the combination as determined from the dose escalation portion of the study.

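### Study Calendar footnote 8 starts Arm A pembrolizumab one cycle early, reverses the drug order in Arm B, and gives the pembrolizumab lead-in to a Cohort C that is not in this trial

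*Combined protocol and SAP*

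**What the plan says.** Section 5.2 sets the treatment order for two arms, in both escalation and expansion. In Arm A, trametinib starts at C1D1, and for escalation the text continues: "Pembrolizumab will be added to trametinib starting C2D1". For the other arm it reads: "Dose Escalation Cohort (Arm B): Pembrolizumab will be administered starting C1D1 and trametinib will be added to pembrolizumab starting C2D1". Section 5.2.1.1, the cohort table in Section 5.3 and Section 8.0 agree: Arm A has a trametinib lead-in, Arm B a pembrolizumab lead-in, and the combination begins in cycle 2.

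Footnote 8 of the Study Calendar (Section 6.0) is attached to the row for trial treatment administration. After an opening sentence on the maximum duration of pembrolizumab, it gives three schedules:

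- Arm A, escalation and expansion, described as concurrent: "both drugs will be administered as outlined in this protocol starting with cycle #1".
- Cohort B: "For cohort B. trametinib will be initiated with cycle #1 and pembrolizumab (MK-3475) will commence in combination with trametinib starting with cycle #2".
- Cohort C: "for Cohort C pembrolizumab (MK-3475) will be given for cycle 1 with concurrent trametinib added on C2D1".

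Footnote 1 of the same calendar requires weekly visits in the cycle "when trametinib is added (Cohort A C1D1, Cohort B C2D1"), which matches Section 5.2 and not footnote 8.

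**The concern.** The order of the two drugs is the variable on which the arms differ. Section 3.3 hypothesises that the trametinib lead-in is the more promising, and Section 8.0 uses toxicity, response, PFS and immune correlates to decide which sequence to take forward. A footnote on the treatment row that gives Arm A no lead-in and gives Arm B the Arm A order would, if followed, blur or swap that contrast.

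The footnote could plausibly be followed. Section 7.1.4.2 says nothing about the treatment period except to refer the reader to the calendar. Table 2 in Section 5.2 does not separate the arms, so it would not alert someone who had read the footnote first. The trial is multisite.

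**Working it through.** The plan states no figure to reproduce. The check sets the texts side by side and then counts exposure.

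**Start cycle by arm and drug**

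| Arm, drug | Sections 5.2 and 5.2.1.1 | Footnote 8 | Difference |
|---|---|---|---|
| A, trametinib | cycle 1 | cycle 1 | none |
| A, pembrolizumab | cycle 2 | cycle 1 | one cycle early |
| B, pembrolizumab | cycle 1 | cycle 2 | one cycle late |
| B, trametinib | cycle 2 | cycle 1 | one cycle early |

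Three of four entries are wrong, each by one 21-day cycle. The footnote gives Cohort C the schedule that Section 5.2 gives to Arm B. The trial summary, Section 5.3 and Section 8.0 define two arms, with 12 patients in each expansion cohort, and none of them defines, sizes or analyses a Cohort C.

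**Exposure per patient over cycles 1 and 2**

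This is the six-week DLT period of Section 5.4. Table 3 gives trametinib on D1-D10 at dose levels 1 and 2 and on D1-D7 at level -1. Pembrolizumab is one infusion per cycle.

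- Trametinib days = days per cycle × number of cycles with trametinib.
- Infusions = number of cycles with pembrolizumab.
- Concurrent cycles = number of cycles with both drugs.

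| Schedule | Trametinib days, levels 1 and 2 | Trametinib days, level -1 | Infusions | Concurrent cycles |
|---|---|---|---|---|
| Arm A, planned | 10 × 2 = 20 | 7 × 2 = 14 | 1 | 1 |
| Arm A, footnote 8 | 10 × 2 = 20 | 7 × 2 = 14 | 2 | 2 |
| Arm B, planned | 10 × 1 = 10 | 7 × 1 = 7 | 2 | 1 |
| Arm B, footnote 8 | 10 × 2 = 20 | 7 × 2 = 14 | 1 | 1 |

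The last row equals the first: an Arm B patient dosed by footnote 8 receives the planned Arm A regimen.

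The choice of window matters. The opening of Section 8.0 bases escalation on DLTs in cycle 2, although it later refers to a 6-week DLT period. In cycle 2 alone both drugs are given under either text in both arms, so the dose counts do not differ; only the exposure before cycle 2 does.

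**DLT evaluability.** Section 5.4 requires a completed lead-in plus concurrent dosing. An Arm A escalation patient dosed by footnote 8 has no lead-in and fails that requirement. An Arm B patient so dosed has had a lead-in and a concurrent cycle, so that requirement would not exclude the patient. Whether the 80%-of-planned-treatment rule would do so depends on how it is counted, which Section 5.4 does not say; counted by drug, pembrolizumab would be 1 of 2 planned infusions, or 50%.

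**Weekly visits.** Footnote 1 starts Arm B trametinib at C2D1 and footnote 8 starts it in cycle 1. Both cannot be followed.

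**On-treatment biopsy.** Footnote 9 says: "Repeat biopsy will be performed on cycle 1 D11-13 or within 2 days after the last dose of trametinib for Arm A". Under the plan, the cycle 1 sample reflects trametinib alone in Arm A and pembrolizumab alone in Arm B. Under footnote 8 it would reflect both drugs in Arm A and trametinib alone in Arm B.

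**The case against.** The strongest reply is that this is one labelling slip. Footnote 8 describes both of the trial's regimens correctly but labels them B and C instead of A and B, with an unused concurrent regimen under A; counting three wrong start cycles makes one slip look like several. Cohort C also signals the error to a careful reader. Section 7.1 describes the calendar as a summary, and Section 5.2 is where treatment is specified. The slip may well have a single origin, such as a leftover from a three-arm design, but that is inference. The labels are what tell a site which schedule a patient receives, so the instruction is wrong for both arms whatever its origin. The footnote's reference back to the protocol does not rescue the Arm A clause, which still calls the regimen concurrent and starts both drugs in cycle 1.

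A second objection concerns evaluability and replacement. The formal definition in Section 5.4 turns on six weeks of treatment and 80% of planned treatment, which an Arm A patient dosed by the footnote might meet. That is fair as a reading of one sentence, but the preceding paragraph makes the lead-in mandatory. On replacement the objection stands in part: the Section 8.0 rule covers escalation patients who discontinue and are not evaluable, and Section 5.9 gives no replacement strategy, so replacing a patient still on treatment rests on Section 5.4.

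Third, there are safeguards: a call with all centres when the last patient in each cohort completes DLT assessment, meetings of the principal investigator and coordinator at least monthly (Section 10.5), central registration (Section 11.1), and treatment-cycle forms within 14 days and deviation notices within 2 days (Section 11.2). Most of footnote 1's weekly-visit rule is worded by actual dosing, so much of that monitoring would follow the patient. These make prolonged undetected misdosing unlikely, particularly in escalation. They limit the harm but do not make the footnote correct.

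**Conclusion.** The inconsistency is real and should be fixed. Footnote 8 contradicts Sections 5.2, 5.2.1.1, 5.3 and 8.0 for both arms, and footnote 1 of its own calendar for Arm B. Three of four start cycles are wrong, each by 21 days, and one schedule is assigned to a cohort the trial does not have.

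The consequence is conditional on a patient being dosed by the footnote; no count of affected patients can be given. In escalation, such an Arm A patient would need replacing, at the cost of extra enrolment and delay rather than a lost 3+3 decision. Such an Arm B patient would contribute DLT and response data that describe the Arm A sequence. In either arm the cycle 1 biopsy would sample the wrong exposure. The exposure counts assume the six-week window of Section 5.4 and full dosing at the stated level. No alpha, power or sample-size figure is affected.

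**What to change.** Keep the first sentence of footnote 8, "Pembrolizumab (MK-3475) can be administered for up to 2 years", and replace everything after it with:

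> For dose escalation and expansion: Arm A: trametinib from C1D1, pembrolizumab added C2D1. Arm B: pembrolizumab from C1D1, trametinib added C2D1.

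This removes Cohort C and brings the footnote into line with Section 5.2 and footnote 1. The cost is close to nil: one footnote is rewritten, with no change to design, sample size, procedures or the two-year pembrolizumab limit.

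Two clerical corrections could be made at the same time; the finding does not rest on them. Section 8.0 refers to three sequencing schemes where there are two, and Section 4.3.2 contains a sentence on Cohorts A to D at 10 mg/kg Q2W, a dose and schedule this trial does not use.
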